## Additional analyses for drug-induced liver injury

The following additional analyses will be performed for drug-induced liver injury:

- For each liver function test (eg, ALT), participants having experienced a PCSA will be summarized considering worst on-treatment value.
- An e-DISH-like plot of peak bilirubin/ULN versus peak alanine aminotransferase or aspartate aminotransferase (worst value)/ULN will be provided. The graph will be divided into 4 quadrants with a vertical line corresponding to 3 ULN for ALT/AST and a horizontal line corresponding to 2 ULN for total bilirubin.
- For each liver function test (eg, ALT), participants having experienced a PCSA (eg, ALT >5 x ULN) will be summarized using the following categories: Returned to baseline PCSA status (or returned to value ≤ULN in case of missing baseline) before last IMP dose, Returned to baseline PCSA status after last IMP dose, Never returned to baseline PCSA status, No assessment after elevation. This summary will be performed by categories of elevation (ALT >3, >5, >10, >20 x ULN).

### 3.6.3.2 Ophthalmological examinations

#### Schirmer test

Participants reported Schirmer's test will be classified into 3 classes at baseline: normal ( $\geq 10 \text{ mm}$ ), moderate (<10 and >5 mm), severe ( $\leq 5 \text{ mm}$ ) (3). The worst classification between the laterality will be considered. A frequency table of the baseline status with and without anaesthetics will be provided for the participants with corneal events (CMQ) during the treatment-emergent period and for the participants without an event.

#### Visual acuity test

Analyses are done on the best corrected visual acuity (BCVA) assessed using Snellen Chart method.

Frequency tables on BCVA measured during the on-treatment period will be performed separately on all participants and on participants who experienced at least one treatment-emergent corneal event:

- On the worst change from baseline: No worsening versus baseline (no line decrease), Worsening versus baseline (1 to 3 lines decrease versus baseline, or >3 lines decrease versus baseline).
- On the worst absolute value: No change versus baseline, Worsening versus baseline (BCVA equals to 20/40 or better, BCVA worse than 20/40 up to 20/200, BCVA 20/200 or worse).
- On the CTCAE worst vision decrease: BCVA equals to 20/40 or better or 1 to 3 lines decrease versus baseline, BCVA worse than 20/40 up to 20/200 or >3 lines decrease versus baseline, BCVA 20/200 or worse.

• For participants who had worsening versus baseline (at least one line decrease) on BCVA, the worst outcome on the last BCVA will be displayed: Recovered to baseline, Not recovered to baseline, Lost to follow-up or dead with ongoing corneal events.

A participant will be considered as lost to follow-up if the participant discontinued the study and did not perform any follow-up visit.

A shift table of the category of the last BCVA value (Normal (20/20 or better), worse than 20/20 up to 20/40, worse than 20/40 up to 20/200 or 20/200 or worse) versus the category of the worst BCVA value (20/40 or better, worse than 20/40 up to 20/200, 20/200 or worse) will be performed for participants who experienced at least one treatment-emergent corneal event.

For the summary table on participants who experienced at least one treatment-emergent corneal event, the worst value and the worst change from baseline are measured during any of the treatment-emergent corneal events experienced by the participant (between start date and end date of the corneal events). For summary table on all participants, all on-treatment BCVA values are considered.

The worst classification between the laterality will be considered for the worst absolute value, the worst change from baseline and the last value separately even if not measured on the same eye. If the worst absolute value is the same for both eyes, then the eye with the worst change from baseline is considered, and if identical, then the eye with the worst last value is considered.

Participants whose baseline visual acuity had been reported in naked eye instead of BCVA (ie, whenever the baseline value was worse than the values reported during the treatment period/treatment-emergent corneal event) will be excluded from this analysis.

# Slit lamp examination

Descriptive statistics of slit lamp examination will be provided separately at baseline and at the time of first abnormal slit lamp after occurrence of a treatment-emergent corneal event, and at the time of the worst BCVA value during a treatment-emergent corneal event for participants experiencing treatment-emergent corneal events (CMQ). The outcome (normal, abnormal), and for abnormal findings, the type of lesions and the distribution will be described by laterality (unilateral, bilateral, all).

# 3.7 OTHER ANALYSES

# 3.7.1 Other variables and/or parameters

# 3.7.1.1 PK analyses

All concentration values below the LLOQ will be treated as zero in individual listing and respective descriptive statistics. Geometric mean will not be computed in case at least one concentration is below LLOQ.

Individual observed predose concentrations ( $C_{trough}$ ) and concentrations observed at end of infusion ( $C_{eoi}$ ,  $C_{eoi+1h}$  if any) of tusamitamab ravtansine and ramucirumab will be listed and summarized with standard descriptive statistics (such as the number of observations, arithmetic and geometric means, median, standard deviation, coefficient of variation, minimum, and maximum) by visit and by dose level (if applicable).

For the descriptive statistics,  $C_{trough}$  following any dose modification (delay or reduction as defined in Section 3.6.1.2) will be excluded.  $C_{eoi}$  and  $C_{eoi+1h}$  will be excluded following dose reduction.

A graphical representation of mean  $C_{trough}$  ( $\pm$ SD) profile over time, by drug in separate figure and by dose level superimposed in the same figure (if applicable), will be provided throughout the course of treatment.

# 3.7.1.1.1 Population PK analyses

The population PK analyses will be described in a specific document and the results will be presented separately from the clinical study report.

# 3.7.1.1.2 lgG

In the all-treated population, the level of IgG in blood at pre-infusion of Cycle 1 Day 1 will be summarized with standard descriptive statistics (such as the number of observations, arithmetic and geometric means, median, standard deviation, coefficient of variation, minimum and maximum) for tusamitamab ravtansine. A listing will also be provided.

# 3.7.1.2 Immunogenicity analyses

Participant's ATA status, response variable, and kinetics of ATA responses (see definitions below) will be summarized on the ATA population.

Kinetics of ATA responses will be described for participants with treatment-induced ATA and for participants with treatment-boosted ATA, separately. Time to ATA onset and duration of ATA will be described with minimum, Q1, median, Q3, and maximum statistics.

Peak titer will be described with minimum, Q1, median, Q3, and maximum statistics for participants with treatment-induced ATA and for participants with treatment-boosted ATA, separately.

Sample status (negative, positive, inconclusive) and titers will also be described overtime using descriptive statistics.

The impact of positive immune response on efficacy, PK, and safety variables may be further explored, depending on ATA incidence.

# Participant's ATA status

- Participants with **pre-existing ATAs** correspond to participants with ATAs present in samples drawn before first administration of intervention. Participants with missing ATA sample at baseline will be considered as without pre-existing ATA.
- Participants with **treatment-emergent ATA** correspond to participants with at least 1 treatment-induced/boosted ATA.
  - Participants with **treatment-induced ATAs** correspond to participants with ATAs that developed at any time after first IMP administration and without pre-existing ATA (including participants without pre-treatment samples).
  - Participants with **treatment-boosted ATAs** correspond to participants with preexisting ATAs that are boosted at any time after first IMP administration to a significant higher titer than the baseline. A 2-fold serial dilution schema is used during titration, so at least a 4-fold increase will be considered as significant.
- Participants with **unclassified ATA** correspond to participants with pre-existing ATAs that cannot be classified as treatment-boosted ATA because of missing titer(s) (ie, a positive ATA sample at any time after first IMP administration in a participant with pre-existing ATA but with missing titer at this sample or at baseline).
- Participants without treatment-emergent ATA correspond to participants without treatment-induced/boosted ATA and without any inconclusive sample nor unclassified ATA at any time after first IMP administration.
- Participants **with inconclusive ATA** are defined as participants which cannot irrefutably be classified as with or without treatment-emergent ATA.

#### Kinetics of ATA response

Kinetics of ATA response will be derived for participants with treatment-induced/boosted ATA.

- **Time to onset of ATA response** is defined as the time period between the first IMP administration and the first treatment-induced/boosted ATA.
- **Duration of ATA response** is defined as the time between the first treatment-induced/ boosted ATA and the last treatment-induced/boosted ATA, irrespective of negative samples or positive samples not reaching the boosted threshold in-between. ATA duration will be summarized only for participants with persistent ATA response.
- **Persistent ATA response** is defined by treatment-induced/boosted ATA with a duration of ATA response of at least 16 weeks.
- **Transient ATA response** is defined by treatment-induced/boosted ATA with a duration of ATA response of less than 16 weeks and the last sample is not treatment-induced/boosted.
- **Indeterminate ATA response** is defined by treatment-induced/boosted ATA that are neither persistent nor transient.

# ATA response variable:

• ATA incidence is defined as the proportion of participants found to have seroconverted (treatment-induced ATAs) or boosted their pre-existing ATA response (treatment-boosted ATAs) at any time after first IMP administration.

## 3.7.1.3 Biomarker analyses

Several exploratory objectives related to pharmacodynamic endpoints will be considered in this study.

The circulating CEA will be considered as a quantitative variable or as a binary variable when considering different binary thresholds: <3, <5, <50, <80 or  $<100 \mu g/L$ .

Circulating CEA values below the LLOQ will be replaced by half of the LLOQ.

### 3.7.1.3.1 Circulating CEA levels before IMP and CEACAM5 IHC

In the pre-screened population, the CEACAM5 IHC expression status (negative (0%), moderate (1-49%) and high expressers ( $\geq$ 50%) based on the % of cells expressing CEACAM5 at the membrane with intensity >= 2+) and the H-score will be described using descriptive statistics.

Circulating CEA levels before IMP will be correlated with IHC CEACAM5 expression status (for prescreened participants). To this end, the closest circulating CEA assessment to biopsy (or the oldest value before IMP if the date of the biopsy is missing) will be considered. The circulating CEA levels (quantitative and by thresholds) will be presented using descriptive statistics by IHC CEACAM5 expression status (negative, moderate and high CEACAM5 expressers) and overall.

The correlation between the circulating CEA levels (quantitative) and the IHC CEACAM5 expression will be also assessed, and graphically visualized. To this end, Pearson correlation, Spearman's rank, or Kendall's tau coefficient will be considered depending on the nature of the data. The time between the tumor biopsy specimen collection date and the date of the considered circulating CEA assessment will also be described and investigated in the correlation.

To evaluate the variability of circulating CEA values before IMP, an intraclass correlation coefficient will be calculated between circulating CEA values (when two values are available). A graphical visualization may be provided to observe the degree of concordance.

#### 3.7.1.3.2 Circulating CEA levels at baseline and clinical response

Circulating CEA levels before IMP administration will be correlated with confirmed objective response (for all treated participants). To this end, the last circulating CEA assessment before (closest to) IMP administration will be considered and reported as the baseline value.

Baseline circulating CEA values will be presented using descriptive statistics by response status and overall. The confirmed objective response rate and two-sided 95% CIs using the Clopper-Pearson method will be presented for each circulating CEA subgroups (base on the predefined thresholds).

The correlation between the circulating CEA levels (quantitative) and the tumor burden at baseline will be also assessed and visualized graphically. To this end, Pearson correlation, Spearman's rank, or Kendall's tau coefficient will be considered depending on the nature of the data.

# 3.7.1.3.3 Modulations of circulating CEA as a potential PD biomarker of response to tusamitamab ravtansine treatment

A graphic visualization (spaghetti plot) will show the relative change from baseline of circulating CEA values for each participant, and will be annotated with the BOR.

# 3.7.1.3.4 Mutational profiling

Genomic alterations locally assessed and entered in the eCRF at prescreening as per protocol will be presented. For each gene, participants will be grouped into two groups: "altered" (ie, participants with at least one alteration for the gene) and "wild-type" (ie, participants without alteration for the gene) and described using descriptive statistics by IHC CEACAM5 expression and overall. The confirmed objective response rate and two-sided 95% CIs using the Clopper-Pearson method will be presented for each gene in the all-treated population.

Circulating-free DNA (cfDNA) centrally assessed may be also generated and will be analyzed in the same way as genomic alterations entered locally in the eCRF.

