- c **D1 predose:** Cycle 1 D1 refers to the day the participant receives the initial dose of IMP. D1 of Cycle 2 and of each subsequent cycle corresponds to D15 of the previous cycle. During treatment, D1 assessment can be done on the day of infusion (before infusion) or the day before. C1D1 hematology, blood chemistry, coagulation and urinalysis tests may be omitted if baseline test performed within 7 days are normal. If baseline tests are abnormal should be repeated within 2 days of first study intervention.
- d **Follow-up visit:** SAEs/AESIs (regardless of relationship with study treatment) and IMP-related AEs ongoing at the end of study treatment, and any new IMP-related AE/SAE/AESI will be followed until resolution or stabilization (defined as an event ongoing without any change for at least 3 months). Date of disease progression and further anticancer treatment will be collected at the follow-up visit. Participants who stopped treatment before documented progressive disease (PD; ie, achieving stable disease [SD] or complete or partial response [CR or PR]) should undergo a tumor assessment and an on-site follow-up visit every 8 weeks (± 7 days) after the last tumor assessment until radiological disease progression, death, cut-off date for secondary endpoints, initiation of further anticancer therapy, or withdrawal of the participant's consent, whichever comes first. Participants with documented disease progression should attend an on-site follow-up visit 90 days after the last dose of study medication. If every ongoing related AE/SAE/AESI is resolved or stabilized, no further follow-up visit is needed; otherwise an on-site follow-up visit will be performed every 12 weeks after the End of Treatment visit until resolution of the event.
- e **Disease history** includes previous antitumor therapy (type, start and end dates, reason for discontinuation and response to the therapy).
- f **Tumor characteristics:** data collected will include histologic types, stage at diagnosis, disease extent at study entry; known specific mutations (*BRAF*, *KRAS*, *NRAS*, *PIK3CA*, *PTEN*, *PTP53*, *CCDN1*, *NTRK1*, *NTRK2*, *NTRK3*), known HER2 and MET status (data collected at screening) and known PD-L1 expression (data to be collected only at prescreening).

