8.5 GENETICS

A 20 mL blood sample corresponding to about 10 mL of plasma and an additional 2 mL blood sample for germline DNA will be collected for future use at pre-infusion of Cycle 1, Day 1. These samples may be used for but not restricted to tumor circulating free deoxyribonucleic acid (cfDNA) and germline DNA isolation respectively. Other blood and plasma components as circulating proteins or RNA may be also evaluated.

Participants who do not wish to participate in the genetic research may still participate in the study.

In case of cfDNA/DNA isolation, samples are planned to be transferred to a central laboratory for extraction and mutational profiling of key cancer genes to understand the significance of existing mutation during tusamitamab ravtansine treatment.

Fragmented circulating tumor DNA or cfDNA is released from the tumor in the plasma and can readily be extracted and analyzed for mutation of common cancer genes. Subtractive mutation analysis will be performed with germline DNA data to identify tumor specific somatic genetic aberrations. The list (not exhaustive) of the genes that could be mutated/translocated is: *AKT1*, *ALK*, *BRAF*, *CDKN1B*, *CDKN2A*, *CDKN2D*, *EGFR*, *ESR1*, *FGFR4*, *HER2*, *HRAS*, *KRAS*, *MDM2*, *MED1*, *MET*, *NRAS*, *PIK3CA*, *PTEN*, *RBI*, *RET*, *ROS1*, and *TP53*.

See Appendix 5 ([Section 10.5](#)) for information regarding genetic research. Details on processes for collection, shipment and destruction of these samples can be found in the study laboratory manual.

As new knowledge is acquired about the disease and/or tusamitamab ravtansine, other techniques could be implemented to evaluate other analytes such as circulating proteins or RNA.

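### The two-group gene rule in SAP 3.7.1.3.4 has no place for participants not tested for a gene; read literally, they are counted as wild-type

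*SAP*

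**What the plan says.** SAP 3.7.1.3.4 (Mutational profiling) starts from local results: "Genomic alterations locally assessed and entered in the eCRF at prescreening as per protocol will be presented". It then sets the rule: "For each gene, participants will be grouped into two groups". One group is altered, meaning at least one alteration in the gene. The other is wild-type, meaning "participants without alteration for the gene". ORR with a two-sided 95% Clopper-Pearson interval "will be presented for each gene in the all-treated population".

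The same section allows a second source. "Circulating-free DNA (cfDNA) centrally assessed may be also generated", and those data are to be analysed in the same way as the local results.

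The gene data are specified in footnote f of the flow chart in Protocol 1.3.1: "data collected will include histologic types, stage at diagnosis, disease extent at study entry; known specific mutations", followed by a list of ten genes. Protocol 8.5, on the blood samples that may be used for cfDNA and germline DNA, adds: "Participants who do not wish to participate in the genetic research may still participate in the study".

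**The concern.** Wild-type is a residual group: it is defined by the absence of an alteration, not by a negative test result. The data source holds only what is already known from local practice. For some participants and some genes the status will probably be unknown, and the written rule offers no category for that.

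Three planned outputs are exposed:

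- the frequency of each alteration, because untested participants sit in the denominator;
- the wild-type ORR and its exact interval, because the interval width depends on a count that includes people with no result for the gene;
- the contrast between altered and wild-type, which can be diluted if some untested participants carry the alteration.

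**Working it through.** **Does the text lead there?** The documents state no share tested, no alteration prevalence and no ORR by gene, so there is no figure of the plan's own to reproduce. The first step is to read the provisions together.

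1. SAP 3.7.1.3.4 names two groups per gene and no third.
2. Wild-type requires no alteration. It does not require a test.
3. ORR by gene is placed in the all-treated population, with no restriction to participants tested for that gene.
4. Protocol 1.3.1, footnote f, collects known mutations. The only tumour marker test required for entry is central CEACAM5 immunohistochemistry (Protocol 5.1, I 06). No section requires local testing of the listed genes.
5. Central cfDNA is optional in the SAP, and the underlying sample is optional in the Protocol 1.3.1 flow chart.

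From 1 to 3, an untested all-treated participant has only the wild-type group to fall into. From 4 and 5, such participants are to be expected.

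**How far are the denominator and interval affected?** All counts below are assumptions, not trial data. Take N = 32, the planned number evaluable for activity (SAP section 4). Suppose 16 are tested for a gene (4 altered, 12 negative) and 16 are not tested.

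- Wild-type denominator as written: 12 + 16 = 28. Among those tested: 12.
- Alteration frequency as written: 4/32 = 12.5%. Among those tested: 4/16 = 25.0%.

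Let response be unrelated to both mutation and testing, at 25% throughout: 3/12 in tested negatives and 4/16 in untested.

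| Wild-type group | Responders | ORR | 95% Clopper-Pearson | Width |
|---|---|---|---|---|
| As written | (3 + 4)/28 = 7/28 | 25.0% | 10.7% to 44.9% | 34.2 points |
| Tested only | 3/12 | 25.0% | 5.5% to 57.2% | 51.7 points |

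The rate does not move, but the interval is narrower than 12 tested participants can support.

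If untested participants respond less often, say 2/16 = 12.5%, the wild-type rate as written is (3 + 2)/28 = 17.9% (6.1% to 36.9%). It stays at 25.0% among those tested. That shift comes from the assumed difference by testing status.

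**How far can undiagnosed alterations move the rate?** Let p be the true alteration prevalence and t the share tested, with testing unrelated to mutation. Let a and w be the true ORRs in altered and wild-type participants.

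- Labelled wild-type = N − N·t·p
- Untested = N(1 − t)
- Hidden altered = N(1 − t)p
- Labelled wild-type ORR = [N(1 − p)w + N(1 − t)p·a] / (N − N·t·p)

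With N = 32, a = 10% and w = 30% (all assumed), the two extremes of the range examined are:

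| p | t | Labelled wild-type | Untested share | Hidden altered share | Labelled wild-type ORR |
|---|---|---|---|---|---|
| 5% | 75% | 30.8 | 8/30.8 = 26% | 0.4/30.8 = 1.3% | (9.12 + 0.04)/30.8 = 29.7% |
| 50% | 25% | 28.0 | 24/28 = 86% | 12/28 = 42.9% | (4.8 + 1.2)/28 = 21.4% |

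With the two ORRs reversed (a = 30%, w = 10%), the labelled wild-type rate rises from 10% to between 10.3% and 18.6%. With everyone tested there is no effect.

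**The case against.** The strongest reply is that the SAP never says in words that an untested participant is wild-type.

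- The section opens with locally assessed alterations, and wild-type ordinarily means a test result. If the eCRF has a not-done or unknown field, untested participants may simply drop out. The eCRF is not among the documents.
- Where this SAP wants missing data assigned to a category, it says so: for a missing baseline ATA sample (3.7.1.2), a missing BOR (3.2.2.1) and a missing causality assessment (3.6.2). It does not do so here.
- Naming the all-treated population need not mean that everyone is classified. IgG is summarised in that population too (3.7.1.1.2), and nobody would assign a value to a participant without a sample. PD-L1 has two-level categories without an unknown level (3.7.2), yet an untested participant would not be read as below 1%.

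This shows that a benign reading is available and may be what is intended. It does not remove the problem: the PD-L1 levels describe a measured value, whereas wild-type is worded as the absence of a finding, which an untested participant satisfies.

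A reader might also infer that the ORR by gene must be wrong, or that any gene-response association would be hidden. The documents support neither. Labels in the altered group stay correct, although the group may be incomplete. The wild-type rate moves only under the conditions shown above.

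A striking example is easy to construct. With 4/12 responders in tested negatives and 2/16 in the untested, the rate falls from 33.3% to 6/28 = 21.4%. Most of that fall comes from the low response assumed in the untested. If testing is instead unrelated to mutation, 25% prevalence among the 16 untested gives 12 wild-type (4 responders expected) and 4 altered. Even with no responders among those 4, the rate is (4 + 4)/28 = 28.6%.

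**Conclusion.** The point holds as a minor one. Followed literally, SAP 3.7.1.3.4 places untested participants in the wild-type group. Whenever some are untested, this overstates the wild-type denominator, understates the alteration frequency if anyone tested is altered, and gives an exact interval too narrow for the number tested. It can dilute an association. Bias in the ORR is conditional: it needs response to differ by mutation or testing status, and it is small for rare alterations. Its size cannot be derived from the documents, and every rate above rests on assumed counts.

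The consequence is limited. Mutational profiling is not a listed objective or endpoint, the study tests no hypothesis, and the primary ORR is unaffected. Small groups limit the comparison under either rule: one responder among 4 altered participants gives 25.0% with a 95% interval of 0.6% to 80.6%.

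**What to change.** Amend SAP 3.7.1.3.4 so that, for each gene:

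- altered means tested, with at least one alteration found;
- wild-type means tested for that gene, with no alteration found;
- all others are reported as not tested/unknown;
- the number tested is shown, and alteration frequency and ORR are computed among those tested;
- the same definitions apply to central cfDNA.

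This takes a sentence or two of text and a check that the eCRF can separate a negative result from no test. The cost is smaller denominators and wider intervals, which reflect the information actually available.
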